## 3 DATA ANALYSIS CONSIDERATIONS

### 3.1 General presentation of summaries and analyses

Statistical analysis and generation of tables, figures, subject data listings, and statistical output will be performed using SAS Version 9.3 or higher. All tables and listings will use Courier New font size 9.

Descriptive statistics will be displayed to provide an overview of the study results. For categorical variables, the number and percentage of subjects in each category will be presented. Unless otherwise noted, all percentages will be displayed to 1 decimal place. No percentage will be displayed for zero counts, and no decimal will be presented when the percentage is 100%. For continuous variables, descriptive statistics will include number of subjects with available measurements (n), mean, SD, median, minimum, and maximum.

Decimal places for descriptive statistics will always apply the following rules:

- “n” will be an integer
- Mean, SD, and median will use one additional decimal place compared to the original data
- Minimum and maximum will have the same number of decimal places as the original value.

Unless otherwise specified, statistical tests of efficacy variables will be presented as two-sided p values rounded to three decimal places. P-values less than 0.001 will be presented as “<0.001” and p-values greater than 0.999 will be presented as “>0.999.” Statistical comparisons will be two-sided and will be performed at the 0.05 level of significance.

A complete set of data listings containing all documented data as well as calculated data (e.g., change from Baseline), as applicable, will be generated.

Treatment groups will be displayed as: Placebo, PSL 50 mg bid, PSL 100mg bid, PSL 200mg bid, and PSL 400mg bid.

Log-transformation is based on natural logarithm. For analyses on log-transformed values, model estimates will be back-transformed to anti-log space for table presentation. See Section 8.1.1 for details.

Data collected at scheduled visits will be included the by-visit summary. Data collected at unscheduled visits will not be included in the by-visit summary, but will be considered when determining the Last Visit, minimum, and maximum post-Baseline values during the Treatment Period. Data collected on Visit 8 will be summarized separately for subjects in the Conversion Period versus the Taper and Safety FU Period.

In general, all CRF data will be presented in the subject listings.

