#### 8.1.1.2 Change in log-transformed seizure frequency from Baseline

The 28-day adjusted seizure frequency value will be log-transformed using the function  $\ln(x+1)$ , where  $\ln$  represents the natural logarithm function. The change in the log-transformed seizure frequency from Baseline is calculated as:  $\ln(SFT+1) - \ln(SFB+1)$ , where SFT corresponds to the seizure frequency during an analysis period and SFB corresponds to the Baseline period seizure frequency.

For the primary efficacy variable for the FDA, SFT and SFB are the observable focal-onset seizure frequency during the 12-week Maintenance Period and Baseline Period, respectively.

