## **8.1.2 Analysis of the primary efficacy variables**

### **8.1.2.1 Primary variable for submission to the US FDA, PMDA, and other regulatory authorities not referencing EMA**

The primary efficacy variable for the US FDA/PMDA is the change in log-transformed observable focal onset seizure frequency from Baseline, over the 12-week Maintenance Period. Analyses of the primary variable for the FDA will be performed on the FAS as described below.

Change from Baseline in observable focal-onset seizure frequency (using the log-transformed data) will be analyzed for the FAS using analysis of covariance (ANCOVA) with treatment group (PSL 400mg bid, 200mg bid, 100mg bid, 50mg bid, and placebo) as the main factor, Baseline log-transformed seizure frequency as a continuous covariate, Baseline SV2A use (Yes or No), and Region (Europe or Non-Europe) as factors. Pairwise contrasts will be constructed to compute estimated effects of each dose from placebo.

Treatment effects will be characterized using treatment differences based on back-transformation of least squares (LS) means obtained from the above ANCOVA model. Percent reduction over placebo will be calculated as  $100 \times (1 - \exp(\text{diff}))$ , where diff is the model estimate of the log ratio between each PSL group and placebo group. Similarly, estimates for the upper and lower bounds of the 95% confidence interval (CI) will be back-transformed for table presentation as  $\exp(\text{lower})$  and  $\exp(\text{upper})$ , respectively, where upper and lower correspond to the 95% CI of the log ratio. If there are issues with convergence, covariates will be dropped sequentially in the order of Region, and then Baseline SV2A use (Yes or No) if further needed.

Pairwise comparisons of the 400mg bid, 200mg bid, and 100mg bid PSL dose groups versus placebo will be carried out using the analysis model described above. Type 1 error will be controlled using the Hochberg step-up procedure (Section 4.5) within SAS® Proc Multtest. If all the results of the 3 pairwise comparisons are statistically significant, then the 50mg bid dose group will be compared to placebo, too. Both multiplicity-adjusted and unadjusted p-values will be presented.

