### **8.1.2.2 Supportive and sensitivity analyses for the primary variable for submission to the US FDA, PMDA, and other regulatory authorities not referencing EMA**

#### **8.1.2.2.1 Sensitivity analysis 1: PPS**

The primary analysis of change from Baseline in observable focal-onset seizure frequency for submission the FDA described in Section 8.1.2.1 will be repeated for the PPS.

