### **8.3.2.1 Change from Baseline in log-transformed observable focal-onset seizure frequency over the first 4 weeks, second 4 weeks, and third 4 weeks of the 12-week Maintenance Period**

The 28-day adjusted seizure frequencies during the Treatment Period will be computed using observed diary records for the following 4-week intervals: Visit 2 to Visit 4, Visit 4 to Visit 5, Visit 5 to Visit 6, and Visit 6 to Visit 7. The 28-day adjusted seizure frequency during the Treatment Period and change from baseline based on the observed data will be summarized descriptively by the 4-week interval.

The change from Baseline in log-transformed observable focal-onset seizure frequency by 4-week interval will be analyzed using a Mixed Model Repeated Measures (MMRM) model, including Baseline log-transformed seizure frequency as a continuous fixed effect covariate, and treatment, Region (Europe or Non-Europe), Baseline SV2A use (Yes or No), and visit as fixed effect factors, and Baseline  $\times$  visit and treatment  $\times$  visit interactions. MMRM assumes that missing data are missing at random and estimates the mean outcome at each time interval by treatment group. An unstructured covariance structure will be used. If the model does not converge, an appropriate covariance structure will be used instead. Estimates of effects and comparison contrasts and CI will be back-transformed for display in tables as described in Section 8.1.2.1.

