## 9.2 Plasma concentrations of concomitant AEDs

Blood samples for measurement of concomitant AED concentrations are collected at Visits 1, 2, 6, and 7. The concomitant AED concentrations will be summarized by visit and treatment group using the same descriptive statistics above (<LOQ values will be excluded) for the AED-PK-PPS. Only AED PK samples taken up to the (date of the last dose of study medication +1) will be included in the summary.

The AEDs investigated with mixed models will be those with data available for at least 10 evaluable subjects in one of the treatment groups (subset of AED-PK-PPS). An evaluable subject is defined as a subject:

- with at least one AED measure (>LOQ) at baseline and at least one AED assessment (>LOQ) during the maintenance period
- who received constant dose of AED for at least 14 days prior to the AED samples

Plasma concentration data for concomitantly administered AEDs (values <LOQ will be excluded) will be assessed by evaluating ratios of steady state levels during the Maintenance Period vs baseline levels. The baseline concentration is defined as the arithmetic mean concentration (if multiple concentrations are available at Visits 1 and 2) or the single concentration (if only 1 concentration is available at Visit 1 or Visit 2). Difference between log-transformed AED concentration at Visits 6 and 7 and baseline will be assessed using Mixed Model Repeated Measures (MMRM). The model will include log-transformed baseline concentration, visit, treatment, and treatment-by-visit interaction as fixed effects. An unstructured covariance structure will be used. If the model does not converge, an appropriate covariance structure will be used instead. Geometric least-squares (LS) means ratios and associated 90% CIs for each visit, by treatment group and PSL total will be calculated by exponentiation of the log-transformed data. Changes in AED concentration during the Maintenance Period and baseline will be considered clinically relevant if the respective 90% CIs fall entirely outside the conventional 0.80-1.25 limits. Forest plots will be provided on these (LS) means ratios and associated 90% CIs.

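### SAP 8.1.2.1 gives the FDA/PMDA primary effect as a percent reduction, but its 95% confidence limits are those of the ratio exp(diff)

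*SAP*

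**What the plan says.** SAP 8.1.2.1 analyses the change in log-transformed seizure frequency by ANCOVA and says in general terms that effects are based on back-transformed least squares means. It then gives one explicit formula for a between-group effect. "Percent reduction over placebo will be calculated as" 100 × (1 − exp(diff)), with diff defined as the model's log ratio of a padsevonil group to placebo.

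The interval comes in the next sentence: "Similarly, estimates for the upper and lower bounds of the 95% confidence interval (CI) will be back-transformed for table presentation as" exp(lower) and exp(upper), "where upper and lower correspond to the 95% CI of the log ratio".

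Two other places bear on how to read this:

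- SAP 3.1 says that, for analyses of log-transformed values, "model estimates will be back-transformed to anti-log space for table presentation. See Section 8.1.1 for details". Section 8.1.1 contains only the forward step ("The 28-day adjusted seizure frequency value will be log-transformed using the function" ln(x+1)), the change and percent reduction from Baseline, and the responder definition. It gives no back-transformation.
- SAP 9.2, on concomitant AED concentrations, names the estimate and its interval together: "Geometric least-squares (LS) means ratios and associated 90% CIs for each visit, by treatment group and PSL total will be calculated by exponentiation".

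Three analyses take over the 8.1.2.1 rule. The per-protocol analysis in 8.1.2.2.1 is the primary analysis "described in Section 8.1.2.1 will be repeated for the PPS". The 4-week-interval MMRM in 8.3.2.1 says: "Estimates of effects and comparison contrasts and CI will be back-transformed for display in tables as described in Section 8.1.2.1". The subgroup analyses in 8.1.2.5 repeat 8.1.2.1 and present estimates with 95% CIs.

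**The concern.** The SAP presents the two rules as analogous, but they put the estimate and its limits on different scales. A percent reduction has no effect at 0, and larger is better. The exponentiated limits of a log ratio belong to a ratio, with no effect at 1 and smaller better. A programmer who follows both sentences literally would set a percent reduction beside an interval for another quantity.

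This is the headline effect size for the FDA/PMDA primary endpoint. It matters most in the subgroups: SAP 4.8 rules out testing there, so the interval is the only measure of uncertainty, and the reader must know which value means no effect.

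**Working it through.** **The algebra.** Let g(x) = 100 × (1 − exp(x)). The SAP's estimate is g(diff). Because g decreases in x, the 95% interval for g(diff) is g(upper) to g(lower), that is, 100 × (1 − exp(upper)) to 100 × (1 − exp(lower)). The bounds swap. The interval exp(lower) to exp(upper) belongs to exp(diff). None of this depends on the data.

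**Inputs for an illustration (SAP 2.7).** Log-reductions are 0.195 for placebo and 0.492, 0.670, 0.754 and 0.780 for 50, 100, 200 and 400 mg bid. The common SD is 0.985, with 80 subjects per arm. As a check on these inputs, simulating the stated success criterion (400 and 200 mg bid, or 200 and 100 mg bid) with Hochberg over the three higher doses and a shared placebo arm gives 91.7% power, in line with the stated 90%. The point itself disputes no stated figure.

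**Standard error.** SE = 0.985 × √(2/80) = 0.1557, without covariate adjustment.

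**400 mg bid, step by step.**

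- diff = −(0.780 − 0.195) = −0.585
- 95% CI of the log ratio: −0.585 ± 1.96 × 0.1557 = −0.890 to −0.280
- SAP effect formula: 100 × (1 − exp(−0.585)) = 44.3%
- SAP limit rule: exp(−0.890) = 0.411 and exp(−0.280) = 0.756
- Limits that match 44.3%: 100 × (1 − 0.756) = 24.4% to 100 × (1 − 0.411) = 58.9%
- Estimate that matches 0.411 to 0.756: exp(−0.585) = 0.557

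**All doses.**

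| Dose (bid) | diff | SAP estimate | SAP limits | Limits matching the percent reduction | Ratio matching the SAP limits |
|---|---|---|---|---|---|
| 400 mg | −0.585 | 44.3% | 0.411, 0.756 | 24.4% to 58.9% | 0.557 |
| 200 mg | −0.559 | 42.8% | 0.421, 0.776 | 22.4% to 57.9% | 0.572 |
| 100 mg | −0.475 | 37.8% | 0.458, 0.844 | 15.6% to 54.2% | 0.622 |
| 50 mg | −0.297 | 25.7% | 0.548, 1.008 | −0.8% to 45.2% | 0.743 |

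**Would a reader notice?** Not always. Read as percentages, the 400 mg bid limits become 41.1% to 75.6%, which contain 44.3%. The 200 mg bid limits become 42.1% to 77.6%, which contain 42.8%. The first would put the lower limit of benefit at 41.1% instead of 24.4%. For 100 and 50 mg bid the misread limits exclude the estimate, so the error would show.

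**Sensitivity (400 mg bid).** A t quantile on 392 df (1.966) gives 24.3% to 59.0%. Scaling the SE by 0.8 gives 28.9% to 56.4%, and by 1.2 gives 19.6% to 61.4%. The widths change; the mismatch of scale does not.

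**Smaller arms, as in subgroups (assumed sizes, 400 mg bid).**

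| Per arm | SE | Ratio limits | Percent-reduction limits |
|---|---|---|---|
| 60 | 0.180 | 0.392 to 0.793 | 20.7% to 60.8% |
| 40 | 0.220 | 0.362 to 0.858 | 14.2% to 63.8% |
| 20 | 0.311 | 0.303 to 1.026 | −2.6% to 69.7% |

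With 20 per arm the interval includes no effect, which is 1 in one column and 0 in the other.

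**The case against.** The strongest reply is that the paragraph means to tabulate a ratio. It opens with back-transformed least squares means, and a back-transformed difference of log-scale means is a ratio. The limits are explicitly tied to the log ratio, so exponentiating them is a valid rule for that ratio. On this reading the percent reduction is an extra derived figure. SAP 3.1 sends model estimates to anti-log space, and 8.3.2.1 treats estimates, contrasts and CIs together as back-transformed. No stated number is wrong, each pair of intervals above is one interval in two notations, and the table shells, which are not in the documents, may already carry a labelled ratio.

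Much of this stands. The limits are correct for a ratio, nothing is lost, and the ratio reading is possible. But no sentence in the current SAP names exp(diff) as a tabulated estimate. The only explicit effect formula is the percent reduction, and the limit rule follows it directly as the analogous step. The pointer in 3.1 leads to a section with no back-transformation, and 8.3.2.1 and 8.1.2.5 lead back to the same paragraph. SAP 9.2 shows how the plan words a ratio when it means to report one.

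**Conclusion.** The concern holds. As written, the limits in SAP 8.1.2.1 do not belong to the only effect estimate for which it gives a formula. At the planning values the two rules give 44.3% with 0.411 and 0.756 for 400 mg bid, where the consistent forms are 44.3% (24.4% to 58.9%) or a ratio of 0.557 (0.411 to 0.756).

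The consequence is limited to reporting. The ANCOVA contrast, p-values, Hochberg decisions and sample size do not change, and the percent-reduction limits can be recovered as 100 × (1 − limit). The mismatch is algebraic and rests on no assumption. The figures rest on the planning means and SD, an unadjusted SE, and assumed arm sizes for the smaller-sample cases; the actual ANCOVA widths will differ. Because the model uses ln(x+1), all these values refer to frequency + 1.

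**What to change.** In SAP 8.1.2.1, choose one form and state it:

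- (a) report the percent reduction with limits 100 × (1 − exp(upper)) to 100 × (1 − exp(lower)), noting that the order reverses; or
- (b) state that the ratio exp(diff) is tabulated and labelled as such, with limits exp(lower) and exp(upper).

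Use the same form in the per-protocol repeat (8.1.2.2.1), the 4-week-interval MMRM (8.3.2.1) and the subgroups (8.1.2.5). In SAP 3.1, change the pointer from 8.1.1 to 8.1.2.1.

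The cost is one sentence, one cross-reference and a check that the table shells use the chosen form. Testing and data are not affected.

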### **8.1.2.2 Supportive and sensitivity analyses for the primary variable for submission to the US FDA, PMDA, and other regulatory authorities not referencing EMA**

#### **8.1.2.2.1 Sensitivity analysis 1: PPS**

The primary analysis of change from Baseline in observable focal-onset seizure frequency for submission the FDA described in Section 8.1.2.1 will be repeated for the PPS.

#### **8.1.2.2.2 Sensitivity analysis 2: multiple imputation**

Multiple imputations will be used to assess the robustness of the primary efficacy analysis results. Multiple imputation will be performed based on log (28-day adjusted seizure frequency +1) by 4-week visit interval over the 16-week Treatment Period. Seizure frequency during a 4-week interval will be calculated as long as seizure data are available for at least 1 day in the given interval.

### Imputation for intermediate missing

Chances of intermittent missing due to completely missing seizure diary during a 4-week interval are low. The intermittent missing seizure frequency before the last 4-week visit interval will be assumed as missing at random (MAR). The intermittent missing data will be filled in using MCMC method with 30 iterations. The imputation model will include treatment groups, log-transformed baseline seizure frequency, baseline SV2A use (Yes or No), region (Europe or Non-Europe), and outcome from each visit interval (in chronological order). Seed=57832.

#### **8.1.2.2.2.1 Sensitivity Analysis 2.1: Missing at random MI**

After the intermittent missing data are imputed, the pattern of the missing data will be monotone. To complete the imputation assuming MAR for each treatment group separately, a regression method using PROC MI statement MONOTONE REG will be used. The imputation model will include explanatory variables for log-transformed baseline seizure frequency, baseline SV2A use (Yes or No), region (Europe or Non-Europe), and outcome from each visit interval (in chronological order). Seed=57832.

Log-transformed seizure frequency during the Maintenance Period will then be computed by taking the average of the data in the three 4-week visit intervals during the Maintenance Period. Multiple imputed datasets will be analyzed using the same ANCOVA model as in the primary analysis. If there are issues with model convergence, covariates will be dropped sequentially in the order of Region, and then Baseline SV2A use (Yes or No) if further needed. The result of the 30 imputed datasets will be combined for overall inference using SAS PROC MIANALYZE.

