## 4.2 Handling of dropouts or missing data

### 4.2.1 Handling of missing data in seizure frequency

Unless noted otherwise, the imputation described below will be applied to seizure frequency. The responder status will be determined based on the imputed seizure frequency data. Sensitivity analyses for missing data are described in Section 8.1.2 for the primary efficacy variable.

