## 8.1 Statistical analysis of the primary efficacy variables

### 8.1.1 Derivations of primary efficacy variables

#### 8.1.1.1 Seizure frequency

Seizure frequency (SF) refers to the 28-day adjusted seizure frequency. The 28-day adjusted seizure frequency is defined as:  $SF = (\text{Number of Seizures}) \times (28 / D)$ . The number of seizures is the total number of seizures during an analysis period or time interval. For cluster seizures, the number of cluster episodes will be included. D corresponds to the number of days for which the diary was available during the analysis period or time interval.

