#### **8.1.2.2.2.2 Sensitivity Analysis 2.2: Control-based MI**

The control-based imputation method used the data from the subjects randomized in the placebo group to impute the missing value for the subjects in the PSL treatment groups. This assumes the subjects on PSL treatment groups will have their efficacy trend toward that of the subjects in the placebo group after the treatment discontinuation. Missing data for the first visit interval are imputed, then missing data for the second visit interval are imputed using observed data and missing data just imputed for the first interval; and so on to the final interval. The imputation will be performed via the sequential regression method using PROC MI statement MONOTONE REG. Multiple imputed datasets will be analyzed using the same ANCOVA model as in the primary analysis. If there are issues with model convergence, covariates will be dropped sequentially in the order of Region, and then Baseline SV2A use (Yes or No) if further needed. Seed=14823.

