#### **8.1.2.2.2.3 Sensitivity Analysis 2.3 Tipping point MI**

Following the National Research Council (NRC) report on missing data (NRC, 2010), a sensitivity analysis using tipping point method to stress-test the result of MAR by imposing a succession of  $\delta$  adjustments, each one more severe, in the PSL Groups until they are no longer statistically significant. This Delta ( $\delta$ ) will be applied just once, at the first visit that has missing frequency seizure data for each subject in the PSL groups who discontinued before the end of treatment period and hence have missing records for "seizure frequencies". Use nimpute = 30, seed = 56432.

The tipping point report (table) for each pairwise comparison will include values for the LSmeans, the 95% CI, and the p-value for each of the delta value (including 0, until p-values are

no longer statistically significant. Only 8 delta values will be tabulated in the report including  $\delta=0$  until  $\delta=xx.x\%$  shift the p-value to larger than multiplicity adjusted alpha level.

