#### **8.1.2.4.3 Sensitivity analysis 3: multiple imputation**

After the multiple imputation process described in Section 8.1.2.2.2, seizure frequency during the Maintenance Period will be calculated as  $[\exp(\log\text{-transformed seizure frequency}) - 1]$  and the 75% responder status will be derived. Multiple imputed datasets will be analyzed using the same logistic regression model as in the primary analysis for the MAR imputation and control-based imputation respectively. If there are issues with model convergence, covariates will be dropped sequentially in the order of Region, and then Baseline SV2A use (Yes or No) if further needed. The tipping point analysis based on MAR multiple imputation will be repeated until

none of the PSL treatment group is significantly different from placebo based on the logistic regression model.

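### The multiple-imputation sensitivity analyses score Maintenance as an average of three interval logs, not the pooled rate of the primary endpoints, so they change the endpoint as well as the missing-data handling, mainly for 75% response

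*SAP*

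**What the plan says.** **Primary endpoints.** SAP 8.1.1.1 defines the 28-day frequency from one count over one set of diary days: "The number of seizures is the total number of seizures during an analysis period or time interval". SAP 8.1.1.2 logs it once, and "SFT and SFB are the observable focal-onset seizure frequency during the 12-week Maintenance Period and Baseline Period, respectively". SAP 8.1.1.4 bases 75% response on the same pooled Maintenance rate.

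**MI analyses.** SAP 8.1.2.2.2 imputes ln(frequency + 1) separately for each 4-week visit interval. SAP 8.1.2.2.2.1 then says: "Log-transformed seizure frequency during the Maintenance Period will then be computed by taking the average of the data in the three 4-week visit intervals". No weighting is given. For responders, SAP 8.1.2.4.3 says: "After the multiple imputation process described in Section 8.1.2.2.2, seizure frequency during the Maintenance Period will be calculated as" exp(log value) − 1.

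The control-based section gives no other Maintenance summary and says "Multiple imputed datasets will be analyzed using the same ANCOVA model as in the primary analysis". The tipping-point section describes itself as "using tipping point method to stress-test the result of MAR".

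**Stated purpose.** SAP 4.2.1: "Sensitivity analyses for missing data are described in Section 8.1.2 for the primary efficacy variable". SAP 8.1.2.2.2: "Multiple imputations will be used to assess the robustness of the primary efficacy analysis results". The SAP does not mention that the summary measure changes.

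**The concern.** A missing-data sensitivity analysis should vary the missing-data assumption and hold the endpoint fixed. Here both change. The primary value is the log of an arithmetic mean rate; the MI value is an unweighted mean of logs, in effect a geometric mean. They agree when the interval rates are equal and in general differ otherwise, even for a subject with a complete diary.

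If the MI result then differs from the primary result, the reader cannot say whether missing data or rescoring caused it. Agreement is equally ambiguous, because the two effects can offset each other. What is at stake is the interpretation of the MI check on the EMA primary endpoint, where a shift in the Maintenance value can move a subject across the 75% line.

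**Working it through.** **1. The plan's own figures.** SAP 2.7 assumes log reductions of 0.195 on placebo and 0.492, 0.670, 0.754 and 0.780 on PSL, SD 0.985 and 80 per arm.
- For 200mg bid the difference is 0.754 − 0.195 = 0.559, which needs 78 per arm for 90% power at two-sided 0.025.
- Simulating Hochberg for the stated success condition at 80 per arm gives 91.5% power. The assumed 75% responder rates give 84.7%. Both agree with the plan, so these inputs are used below.
- SE of a log difference: 0.985 × √(2/80) = 0.156.
- SE of a log OR at 0.121 versus 0.332: √(1/9.68 + 1/70.32 + 1/26.56 + 1/53.44) ≈ 0.42.

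**2. The two definitions.** Let interval k have c_k seizures, d_k diary days and rate r_k = 28c_k/d_k.
- Primary: R = 28Σc_k/Σd_k, scored as ln(R + 1).
- MI: m = (1/3)Σ ln(r_k + 1), with response taken from exp(m) − 1.

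With equal intervals, concavity of the log gives m ≤ ln(R + 1), so MI scoring can only lower the frequency. Intervals run visit to visit (SAP 8.3.2.1) and visits have ±1 week windows (Protocol 8.2.3). With unequal intervals the change can go either way.

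**3. Complete-diary examples.**

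| Baseline | Seizures / days | Primary | MI scoring |
|---|---|---|---|
| 12 | 0, 0, 12 / 28 each | 4.0; 66.7% reduction; non-responder | 13^(1/3) − 1 = 1.35; 88.7%; responder |
| 16 | 4, 4, 4 / 35, 28, 21 | 12 × 28/84 = 4.0; 75.0%; responder | (4.2 × 5 × 6.333)^(1/3) − 1 = 4.10; 74.3%; non-responder |

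**4. Simulation A: completers, nothing missing.** Seizure variability is not in the documents, so it is assumed: baseline median 8, 12 or 20 (log SD 0.9, minimum 4); gamma-Poisson interval counts with dispersion phi 0 to 1.0, equal across arms; arm means and SD as in SAP 2.7. Over 12 scenarios, moving from primary to MI scoring:
- 75% response rises 1.0 to 8.6 points on placebo and 1.5 to 11.0 at 400mg bid.
- The responder difference from placebo rises 0.4 to 2.5 points. The OR falls slightly in all 12 (at most 2.79 to 2.58).
- The log difference moves between 0.009 toward PSL and 0.053 against it.
- In simulated trials of 80 per arm (8 scenarios), the Hochberg verdict per dose (100, 200, 400mg bid) differs in 7.5% to 22.5% for 75% response and 0.4% to 6.3% for ANCOVA.

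A separate simulation with baseline median 6, 10 or 20 and interval CV 0 to 0.8 gave rises of 1.1 to 5.8 points on placebo and 1.9 to 7.4 on active, with at most 0.026 on the log contrast. Its scenario closest to SD 0.985 gave placebo 14.5% to 17.4%, active 32.9% to 37.2%, and OR 2.90 to 2.82.

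**5. Simulation B: with dropout.** Baseline median 12; 10%, 20% or 30% non-informative dropout, uniform over 111 days; carry-forward primary per SAP 4.2.1.2; per-arm MAR MI with 30 imputations; 1,500 trials in each of 12 scenarios. The MI-minus-primary shift is split by also running MI with pooled rates on the same draws.

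| | 75% response (log OR) | ANCOVA (log difference) |
|---|---|---|
| Missing-data part, SD | 0.08 to 0.15 | 0.023 to 0.052 |
| Endpoint part, SD | 0.12 to 0.23 | 0.013 to 0.049 |
| Verdict differs from primary, pooled-rate MI | 6.1% to 12.7% | 2.1% to 5.5% |
| Verdict differs from primary, MI as written | 10.9% to 21.3% | 2.9% to 7.9% |

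For 75% response the endpoint part is the larger in 10 of 12 scenarios. The shift as written has the opposite sign to its missing-data part in 21% to 42% of trials.

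**The case against.** The mismatch in the text is not in dispute. The case against concerns size and remedy.

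- **Dropout pattern.** The 10-of-12 ranking, and probably the opposite-sign figure, depend on uniform, non-informative dropout. Protocol 5.1 withdraws subjects who cannot tolerate IMP before Week 3, so early and unequal dropout is plausible. With an assumed 10% on placebo and 30% on PSL dropping out early, one run gave a missing-data part of 0.29 to 0.32 against an endpoint part of 0.14 to 0.16. Another gave about 0.16 against 0.14 to 0.17. This stands: the ranking is conditional. The endpoint part did not become negligible in either run.
- **Yardstick.** Against an SE of about 0.42, an endpoint SD of 0.12 to 0.23 is roughly 0.3 to 0.55 SE. This stands: it is moderate, not dominant.
- **Verdict changes.** Non-responder imputation keeps the primary definition, yet its verdict differs from primary in 11.3% to 25.4%. Discordance alone therefore proves no defect. The relevant contrast is pooled-rate MI with MI as written, which differ only in scoring.
- **Upper ends.** These rest on phi = 1.0, which no passage supports, and simulated placebo response (15% to 19%) exceeds the SAP's 12.1%. This stands: read the figures as ranges.
- **Existing cover.** The PPS and non-responder analyses keep the pooled definition, and the MI variants are comparable with each other. But the PPS analysis does not impute under other assumptions, and non-responder imputation is one extreme assumption. The MMRM in SAP 8.3.2.1 covers only the log endpoint, assumes MAR and specifies no average-over-Maintenance contrast. None of these bridges 75% response.
- **Scale.** Averaging logs matches the imputation scale, and pooling back-transformed draws has costs. This is fair, and it is why a bridging table is an acceptable alternative.

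**Conclusion.** The concern holds. As written, an MI-versus-primary difference cannot be attributed to missing-data handling alone. That follows from the definitions and needs no simulation.

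It is material for 75% response and small for ANCOVA. Arm-level response can rise by about 1 to 11 points with nothing missing. Much of that cancels between arms on average, but individual trial verdicts can still change. No direction of bias is claimed.

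The sizes rest on assumed seizure variability and equal dispersion across arms, on models without the region and SV2A terms, and on applying Hochberg to the MI analyses, which the MAR and control-based sections do not state explicitly. The component ranking also rests on non-informative, uniform dropout.

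The primary results, their Hochberg testing, and comparisons among the MAR, control-based and tipping-point results are unaffected. The SAP should be changed, but this does not threaten the primary conclusions.

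**What to change.** **Preferred.** Amend SAP 8.1.2.2.2.1, and state that it also governs 8.1.2.2.2.2, 8.1.2.2.2.3 and 8.1.2.4.3. In each imputed dataset, after any delta:
1. Back-transform each Maintenance interval to a rate and floor it at 0.
2. Combine the three as a diary-day-weighted mean, using a nominal 28 days for a fully imputed interval.
3. Apply ln(x + 1) once for the ANCOVA, and the percent-reduction formula for response.

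Since Σ(d_k × 28c_k/d_k)/Σd_k = 28Σc_k/Σd_k, completers then reproduce their primary value exactly.

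**Alternative.** Keep the averaged logs and add one bridging table: the averaged-log endpoint in completers without imputation, beside the primary definition in the same subjects, for both ANCOVA and 75% response. In simulation B this bridging shift correlated 0.80 to 0.97 with the endpoint part for 75% response and 0.39 to 0.95 for ANCOVA.

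**Cost.** SAP wording and minor reprogramming, or one extra table. Pooling has three downsides:
- About 9% to 10% of imputed draws needed the floor in simulation B.
- Back-transformed draws have a heavier upper tail (99.9th percentile 494 to 1051 per 28 days, against 422 to 583 observed), damped by the single log.
- A partly observed dropout interval gets only its diary days as weight.

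**Minor related point.** SAP 8.1.2.2.2 counts an interval with 1 diary day as observed. Day weighting reduces its influence, but only setting very short intervals to missing would bring those subjects under the control-based or delta imputation.
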